CAVUHB	Cardiff and Vale University Health Board
CI	Chief Investigator
CRF	Case Report Form
CTR	Centre for Trials Research
GCP	Good Clinical Practice
GP	General Practitioner
HB	Health Board
HCRW	Health and Care Research Wales
HRA	Health Research Authority
OASIS	Observational study to investigate surgical site infection in ulcerated skin cancers
PI	Principal Investigator
R&D	Research and Development
REC	Research Ethics Committee
SSI	Surgical site infection
UK DCTN	UK Dermatology Clinical Trials Network

1 Amendment History

The following amendments and/or administrative changes have been made to this protocol since the implementation of the first approved version.

Amendment No. (specify substantial/non- substantial)	Protocol version no.	Date issued	Summary of changes made since previous version
Non-substantial	1.2	19/03/19	
p.18: 'type of procedure' added to paragraph 3 ie. data recorded after skin surgery
 
p.22: 'type of procedure' added to list of data recorded on Case Report Form.

Non-substantial	1.3	04/12/19	
p.19:
 
 • 'Whether the participant has been recruited to the study previously' • Number of skin lesions being excised • Number of skin lesions being excised that are ulcerated (if more than one ulcerated lesion, then the patient and researcher should agree on an index lesion for the OASIS study)' 
Above text added to paragraph 1 ie. data recorded before surgery with additional changes highlighted in red below:
 
 • Suspected type of index skin cancer (clinical diagnosis) – to be confirmed on histology

		
 • Site of procedure(s) • Size of index skin cancer (mm) • Size of index tumoral ulceration 
p.22-3:
 
 • 'Whether the participant has been recruited to the study previously • Number of skin lesions being excised • Number of skin lesions being excised that are ulcerated (if more than one ulcerated lesion, then the patient and researcher should agree on an index lesion for the OASIS study)' 
Above text added to list of data recorded on Case Report Form with additional changes highlighted in red below:
 
 • Suspected type of index skin cancer (clinical diagnosis) – to be confirmed on histology • Site of procedure(s) • Size of index skin cancer (mm) • Size of index tumoral ulceration (mm)
--	--	--

List summary of protocol amendments here whenever a new version of the protocol is produced. Ensure details are also updated in a full protocol change log.

[figure not shown]
2 Synopsis

Short title	Observational study to investigate Surgical site Infection in ulcerated Skin cancers
Acronym	OASIS
Internal ref. no.	
Clinical phase	N/A
Funder and ref.	UK Dermatology Clinical Trials Network (UK DCTN) Dermatology Forum for Wales CAVUHB Dermatology Department Research Funds
Study design	Observational prospective study
Study participants	People undergoing surgical excision of ulcerated skin cancer of any type at any body site in the dermatology departments at the University Hospital of Wales Cardiff; Churchill Hospital, Oxford and Queen Elizabeth Hospital, Birmingham.
Planned sample size	311
Inclusion criteria	> 18 years old
Exclusion criteria	
 1) Evidence of wound infection at the time of the procedure 2) Skin tumour removal undertaken curettage or Mohs micrographic surgery 3) People without the capacity to consent for the study 4) People who are on systemic immunosuppressive treatment 5) People who are already taking oral antibiotics
Treatment duration	N/A

Follow-up duration	4 weeks
Planned study period	8 months (recruitment phase) + 1 month (follow-up phase) + 5 months (analysis and write up phase)
Primary objective	To ascertain the proportion of surgical site infections following excision of ulcerated skin tumours in Dermatology Departments.
Secondary objectives	Feasibility work to inform the design of a future randomised controlled trial to investigate whether the use of peri-operative antibiotics in ulcerated skin tumours reduces the proportion of patients with surgical site infection.
Primary outcomes	Proportion of participants with surgical site infection (SSI) identified by postal questionnaire four weeks after surgery.
Secondary outcomes	
a) The proportion of participants, over eight months from screened, eligible and willing to be randomised in a future trial to:
 
 a. no treatment b. topical treatment c. a few days of oral antibiotics d. a week of oral antibiotics 
b) The proportion of participants recruited over eight months from eligible.
 
c) The proportion of participants completing the study (responding to the postal questionnaire) over eight months from eligible.
 
d) Assess feasibility of 'wound selfies' or wound photographs taken in the department as an objective outcome measure.
 
e) The proportion of participants with SSI who were prescribed oral antibiotics at the time of surgery.
 
f) Ulcerated tumour swab analysis results.

Intervention	N/A

3 Study summary & schema

3.1 Participant flow diagram

3.2 Study lay summary

Study title: Observational study to investigate Surgical site Infection in ulcerated Skin cancers (OASIS)

We aim to recruit 311 participants to this study from three UK Dermatology departments. We will invite people with suspected skin cancers whose lesions have a broken surface (also known as ulcerated) who will undergo surgery.

This study is being carried out because it is possible that patients with skin cancers with ulceration might be at greater risk of developing a wound infection after surgery. The aim of this study is to determine how many people with ulcerated skin cancers develop an infection of the wound after it has been surgically removed.

People with ulcerated skin cancers who will have surgery will be invited to participate in the study. If they agree, a member of the research team will explain the study and consent them to participate in the study. At the time of surgery, information will be collected about the participant, skin tumour and procedure. The participant will be given standardised advice

regarding wound care and further care will be as per each centre's 'normal clinical care'. If participants are diagnosed with a wound infection then they will be asked to take a 'wound selfie' and share the photo with the research team. The research team will contact the participant via questionnaire which will be sent four weeks by post or e-mail after the procedure to determine whether they had any concerns about post-operative infection and whether any action was taken.

Additionally, all participants at the University Hospital of Wales will have a surface swab taken from their ulcerated skin cancer and these will be analysed in the Public Health Wales laboratory at the University Hospital of Wales, Cardiff. The aim of this aspect of the study is to identify the most common bacteria in ulcerated tumours.

4 Background

Non-melanoma skin cancer is the most common cancer in the UK with a rising worldwide incidence.¹ For the majority of patients, surgical excision remains the gold standard treatment, however the role of peri-operative antibiotics in preventing post-operative infection remains controversial. Ulcerated tumours occur commonly in dermatological surgical lists ranging from 19-33%.²⁻⁴ In a prospective evaluation of excised skin cancers by our group, including patients undergoing excision at the University Hospital of Wales, Cardiff and the Queen Elizabeth Hospital, Birmingham, one third of skin cancers were clinically ulcerated.

The true proportion of patients developing post-operative infection following surgery in ulcerated skin cancers is needed to determine the sample size for a randomised controlled trial to evaluate the potential benefit of peri-operative antibiotics. Few studies have assessed this accurately although rates of infection have been reported to be as high as 33% in a small single-centre cohort study.² A recently published randomised controlled trial reported SSI in 30% of participants with ulcerated tumours undergoing excision who were not randomised to receive perioperative intravenous cefazolin.⁵ This is significantly higher than quoted figures for all skin cancer excisions (2-8%).⁶⁻⁸ A larger Australian study reported a three-fold increase in the risk of post-operative infection for excision of ulcerated tumours but did not report frequency of SSI.³

Antibiotic resistance is currently one of the most significant threats to patient safety.⁹ Overuse of antibiotics and inappropriate prescribing are well recognized factors which

contribute to antibiotic resistance. Furthermore, a survey of UK Dermatological surgeons, conducted in collaboration with the UK Dermatology Clinical Trials Network (UK DCTN), has shown that there is no agreed consensus on the timing of antibiotic prescribing, choice of antibiotic or length of antibiotic course.¹⁰

To further inform the design of a pilot study, our extended UK DCTN surgical trainee research group has conducted a Critically Appraised Topic to assess the efficacy of perioperative antibiotics in reducing the risk of SSI following excision of ulcerated skin cancers, which confirmed the need for a well-designed RCT to answer this question.¹¹

5 Study objectives/endpoints and outcome measures

5.1 Primary objectives

- To determine the proportion of participants developing SSI following excision of ulcerated skin tumours in three Dermatology Departments: University Hospital of Wales, Cardiff; Churchill Hospital, Oxford and Queen Elizabeth Hospital, Birmingham

5.2 Secondary objectives

- Feasibility work to inform the design of a future randomised controlled trial to investigate whether the use of peri-operative antibiotics in ulcerated skin tumours reduces the proportion of participants with SSI.

5.3 Primary outcomes measure

The main objective is to determine the proportion of participants with SSI within four weeks of surgery. The research team will arrange to contact the participant four weeks after the procedure via a validated questionnaire (see details below) to determine whether they had any concerns about post-operative infection and what action was taken. SSI is broadly defined as the presence of one of the following criteria associated with the wound: abscess, cellulitis, discharge, delayed healing, discolouration, friable granulation tissue, unexpected pain/tenderness, pocketing at base of wound, abnormal smell, wound breakdown.¹² A systematic review has acknowledged the use of several different classifications for SSI and the lack of a standardised tool for diagnosing SSI.¹³ In response to this, Macefield *et al.* have developed a single patient and observer measure for post-discharge SSI assessment and have given us permission to use the tool in this study.¹⁴

5.4 Secondary outcomes measure(s)

- The proportion of participants, over eight months from screened, eligible and willing to be randomised in a future trial to:
 - a. no treatment
 - b. topical treatment
 - c. a few days of oral antibiotics
 - d. a week of oral antibiotics
- The proportion of participants recruited over eight months from eligible.
- The proportion of participants completing the study (responding to the postal questionnaire) over eight months from eligible.
- Assess feasibility of 'wound selfies' or wound photographs taken in the department as an objective outcome measure.
- The proportion of participants with SSI who were prescribed oral antibiotics at the time of surgery.
- Ulcerated tumour swab analysis results

6 Study design and setting

Clinicians in the dermatology department will identify eligible participants at the time of initial consultation in outpatient clinic.

Identification of potential participants will be by the clinical care team, or the clinical members of the research team involved in care of potential participants. Potential participants will be signposted to the research team by the clinical care team.

Patients will be approached by a trained member of the clinical team or research nurse following clinical checks against the inclusion and exclusion criteria. They will be provided with an information leaflet and any other information about the study they request. The patient will be given sufficient information to ensure they fully understand the nature and risks of the study and are given as much time as they require to consider their participation. If they are willing to participate, they will be consented and admitted to the study at the time of surgery. Prior to the procedure relevant clinical information will be recorded in the Case Report Form (CRF) including demographic data, tumour site, tumour size, and size of tumoural ulceration. Participants will be asked whether they would prefer to be contacted via post or e-mail with

the follow-up questionnaire. Histopathological data will be collected on tumour type when it is reported. Participants and clinicians will be asked whether they would agree for the patients to be randomised to no antibiotics, topical treatment eg. Inadine™ dressings, a short course of antibiotics or a longer course of antibiotics in a future RCT. Following the procedure, information about whether oral antibiotics were prescribed will be recorded on a standardized CRF. All participants will be provided with the same information leaflet detailing standard post-operative advice and further care will be as per each centre's 'standard clinical care' which will also be recorded. Standard practice is usually for the patient to contact the local dermatology department where the procedure was carried out, or the patient's local GP practice or for the patient to attend A&E.

If participants are diagnosed with SSI they will be asked to take a photo of their wound on a camera phone and then to share the photo with the Cardiff University Centre for Trials Research (CTR) via email. Reeves *et al.* have described this practice as a 'wound selfie' and report that the term is readily understood.¹⁵ If participants are not able to take of photo of their wound then they will be invited to attend the department to have a photograph taken by medical photography. Including both options will allow us to compare the feasibility of obtaining wound photos via each method. All participants will be sent a questionnaire by the research team four weeks following their procedure by post or by e-mail to enquire specifically whether the participant was diagnosed and treated for wound infection. These data will be collected by Cardiff University CTR who will co-ordinate the study.

Additionally, all participants at University Hospital of Wales will have a surface swab taken from their ulcerated skin tumour and these will be analysed in the Public Health Wales laboratory at the University Hospital of Wales, Cardiff. The aim of this aspect of the study is to identify the most common organisms that colonise ulcerated tumours. Previous studies have commented on growth from ulcerated tumours, however it is not clear if this was conducted in a research laboratory setting.¹⁶ This will help to guide antibiotic choice in a future randomized controlled trial.

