Appendix 1: Questionnaire

Since you left hospital after having surgery.... Response categories

1 Was there redness spreading away from the wound? (erythema/cellulitis) Not at all / A little / Quite a bit / A lot

2 Was the area around the wound warmer than the surrounding skin? Not at all / A little / Quite a bit / A lot

3 Was any part of the wound leaking fluid? Not at all / A little / Quite a bit / A lot

a) Was it clear fluid? (serous exudate) Not at all / A little / Quite a bit / A lot

b) Was it blood-stained fluid? (haemoserous exudate) Not at all / A little / Quite a bit / A lot

c) Was it thick and yellow/green fluid (pus/purulent exudate) Not at all / A little / Quite a bit / A lot

d) I do not know

4 Have the edges of any part of the wound separated/gaped open on their own accord? (spontaneous dehiscence) Not at all / A little / Quite a bit / A lot

a) Did the skin separate? Not at all / A little / Quite a bit / A lot

b) Did the deeper tissue separate? Not at all / A little / Quite a bit / A lot

c) I do not know

5 Has the area around the wound become swollen? Not at all / A little / Quite a bit / A lot

6 Has the wound been smelly? Not at all / A little / Quite a bit / A lot

7 Has the wound been painful to touch? Not at all / A little / Quite a bit / A lot

8 Have you had, or felt like you have had, a raised temperature or fever? Not at all / A little / Quite a bit / A lot (fever <38°C)

9 Have you sought advice because of a problem with your wound, other than at a routine planned follow-up appointment? Yes / No

If yes, please tell us who you sought advice from:

a) A doctor or nurse at the GP surgery/medical centre/walk-in centre Yes / No

b) A doctor or nurse at the hospital Yes / No

c) A midwife or health visitor Yes / No

d) Another health advisor Yes / No

Please describe who the other health advisor was _____

10 Has anything been put on the skin to cover the wound? (dressing) Yes / No

If yes,

a) Was this done by a doctor or nurse at the GP surgery/ medical centre/walkin centre? Yes / No

b) Was this done by a nurse/midwife/health visitor at home? Yes / No

c) Was this done by you/your partner/friend/family member? Yes / No

d) Was this done by a doctor/nurse/midwife at the hospital? Yes / No

e) Please describe what was put on to cover the wound _____

11 Have you been back into hospital for treatment with a problem with your wound? Yes / No

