12 Have you been given antibiotics for a problem with you wound? Yes / No / Don't know

If yes,

a) Were the antibiotics given as tablets/liquid? Yes / No / Don't know

b) Were the antibiotics given via drip? Yes / No / Don't know

If you know the name of the antibiotic(s) you have taken, please write it here _____

13 Have the edges of your wound been deliberately separated by a doctor or nurse? Yes / No / Don't know

14 Has your wound been scraped or cut to remove any unwanted tissue? (debridement of wound) Yes / No / Don't know

15 Has your wound been drained? (drainage of pus/abscess) Yes / No / Don't know

16 Have you had an operation under general anaesthetic for treatment of a problem with your wound? Yes / No / Don't know

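### The protocol says the four-week questionnaire asks about diagnosed wound infection, but no item does, and the wound-photo outcome is left without a denominator

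*Combined protocol and SAP*

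**What the plan says.** Section 6 (Study design and setting) states that all participants receive a questionnaire at four weeks "to enquire specifically whether the participant was diagnosed and treated for wound infection". Section 5.3 describes the same questionnaire more loosely, as a means "to determine whether they had any concerns about post-operative infection and what action was taken", and the lay summary in section 3.2 is similar.

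Appendix 1 gives the questionnaire itself: 16 items under the stem "Since you left hospital after having surgery". Section 5.3 calls it validated and says it is used with its developers' permission.

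On photographs, section 6 says: "If participants are diagnosed with SSI they will be asked to take a photo of their wound". Participants who cannot do this are invited to the department for medical photography, so that the feasibility of the two methods can be compared. Section 11.1 instead ties the photograph to a suspected infection, and the schedule under it heads the column with concern about SSI. Section 5.4 lists the feasibility of wound photographs as a secondary outcome. Section 13.1 says every analysis reports a proportion with a 95% confidence interval.

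**The concern.** If the questionnaire is the stated means of learning whether infection was diagnosed, and it does not ask, that information is lost unless another source holds it. Section 6 says patients usually turn to the dermatology department, their GP practice or A&E, so a diagnosis may be made outside the study sites. The protocol gives no route by which such a diagnosis reaches the coordinating centre.

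The photo outcome depends on the same information. Under section 6 the request follows a diagnosis. Without a record of who was diagnosed, and of who was then asked, a low number of photographs could mean few infections, few requests or few replies. Those explanations have different consequences for using photographs as an outcome measure in the future randomised trial.

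**Working it through.** The plan gives no figure on this point to reproduce. The check is a reading of Appendix 1 and of each listed data source against the stated purpose.

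**Step 1. The 16 items against the two halves of the purpose.**

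| Items | Number | Subject | Diagnosis of infection? | Treatment of a wound problem? |
|---|---|---|---|---|
| 1–8 | 8 | Symptoms and signs | No | No |
| 9 | 1 | Advice sought, and from whom | No | No |
| 10 | 1 | Dressing | No | Not specifically |
| 11–16 | 6 | Return to hospital, antibiotics, wound opening, debridement, drainage, operation | No | Yes |

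Count: 8 + 1 + 1 + 6 = 16. Items on diagnosis: 0 of 16. Items on treatment, re-admission or a wound intervention: 6 of 16.

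The nearest item to a diagnosis is item 9, "Have you sought advice because of a problem with your wound, other than at a routine planned follow-up appointment". It records the contact and not its result. A participant told by a GP that the wound was infected and one told that it was not give the same answer.

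**Step 2. Other listed sources.**

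- Section 11 and section 14.2 list the clinical CRF fields: previous recruitment, lesion counts, type, site and sizes before surgery; type of procedure, Inadine dressing, topical antibiotics and oral antibiotics after it. None is a post-operative diagnosis or a photo request.
- The table in section 14.4 assigns follow-up data to the questionnaire alone. Its photo column holds the photographs received.
- Section 6 says that each centre's further care will be recorded, but no listed field does so.

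**Step 3. The photo outcome.** A yield is photographs received divided by participants asked, or by participants diagnosed. The numerator is available; neither denominator is. To compare the methods one must also know who was asked, who sent a photograph and who had one taken in the department. Only the photographs themselves are listed.

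The primary outcome is not a substitute denominator. At the planning values in section 12.1 it would give about 0.10 × 283 = 28 participants with SSI. Section 5.3 defines that SSI by wound signs, so the group may include people who were never diagnosed and never asked.

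**Step 4. The trigger.** Section 6 makes the request on diagnosis; section 11.1 makes it on suspicion. These are different groups, so even a complete record would give different yields according to the section followed.

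**The case against.** The strongest reply is that the sentence in section 6 is loosely worded. Sections 3.2 and 5.3 describe the questionnaire as covering concerns and action taken, which Appendix 1 does. Section 5.3 defines SSI by wound signs, so the primary outcome as stated needs no clinician's diagnosis. Rewording one sentence would remove the contradiction. This stands for the primary outcome. It does not rescue the photo outcome, where section 6 itself makes diagnosis the condition for a request.

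It can also be said that section 5.4 states a feasibility aim and defines no yield. That is true, but section 13.1 promises a proportion, and section 6 promises a comparison of two methods.

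A third reply is that the CRF lists may be incomplete: the table in section 14.4 places swab results on the CRF, yet neither list has a swab field. The CRF itself is not among the documents, so a diagnosis field cannot be ruled out. The same table, however, does not assign follow-up data to the CRF.

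A reader might infer more than the documents support:

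- **That treatment is unmeasured too.** It is not; items 11 to 16 cover it, for example "Have you been back into hospital for treatment with a problem with your wound".
- **That item 12 counts antibiotics prescribed at surgery and so inflates the SSI rate.** Item 12 asks "Have you been given antibiotics for a problem with you wound", under a stem that starts after discharge. It is limited by both reason and time. Section 5.3 does not list antibiotic use as a criterion, and no scoring rule turns a yes into a case. What remains is possible misreporting by someone finishing a course begun at surgery.
- **That the dressing item, "Has anything been put on the skin to cover the wound", creates false cases.** Nothing in the plan counts a dressing as SSI.
- **That an association with antibiotics would be masked.** Section 13.1 plans no comparison of participants with and without them.

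**Conclusion.** The point holds for diagnosis and for the photo outcome. Section 6 and Appendix 1 disagree: 0 of 16 items ask about a diagnosis, and no listed source supplies it. As written, the plan cannot report photo yield or compare the two photo methods, and its two photo triggers conflict.

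No bias in the primary SSI proportion follows, in either direction, and no number can be put on one. That would need the share prescribed antibiotics at surgery, the share misreporting them and a rule for scoring item 12; the documents give none of these.

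The conclusion assumes that the field lists in sections 11 and 14.2 and the table in section 14.4 describe what is collected. If the CRF in use records diagnoses and photo requests, the remaining faults are the wording of section 6 and the differing triggers.

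**What to change.** After the existing 16 items, with their wording unchanged, add: *Has a doctor or nurse told you that the wound was infected? Yes / No / Don't know. If yes, were you asked for a photograph, and did you send one or have one taken in the department?* Record sending and departmental photography as separate answers.

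Use the participants answering yes as the denominator for photo yield, report how many of them were asked, and give the yield by each method. These figures describe questionnaire responders only and rest on recall.

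Reconcile the photo trigger in sections 6 and 11.1. If suspicion is chosen, the photo question must no longer depend on a yes to diagnosis.

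As an analysis check only, compare yes answers to item 12 with the CRF field on oral antibiotics at surgery. A participant positive on both may be reporting the surgical course or a new one, and the data cannot always separate these. This does not justify rewording items 10 or 12 within a validated tool.

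The cost is one extra question and an amendment. Rewording section 6 alone is cheaper and would remove the contradiction, but it would leave the photo outcome without a denominator.
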